Title: Effect of Soluble Corn Fiber Supplementation for 1 Year on Bone Metabolism in Adolescents

NCT Number: NCT02916862

Date of the document: 09/26/2025

STUDY DESIGN AND METHODS

Study rationale and overall design

The MetA-Bone trial was a double-blinded placebo controlled clinical trial to determine the effects of SCF supplementation for one year on bone mass in children and adolescents. Details of the trial were published elsewhere (25). Briefly, the primary outcome was change in total and spine BMC between baseline and 6 months and between baseline and 12 months. The Institutional Review Board at Florida International University (FIU) approved the study. Also, a Data and Safety Monitoring Board (DSMB) was established and approved by NIH, with yearly meetings to assess safety reports.

Study population

Healthy children and adolescents aged 9-14 years were recruited in the Miami Metropolitan Area. Participants were recruited from various sources from X to X, as previously described (26). We aimed to recruit children and adolescents at a pubertal development (based on Tanner stage) of 2-4 to match the previous study on SCF supplementation for three-week in adolescents conducted by [name] (12). We also aimed to include only those children consuming 2 or fewer servings of dairy products per day, which translates into about 600 mg/d of calcium (half of the recommendation for this age group (27)) and consuming calcium supplements <200 mg/d. Participants were excluded if they had a body mass index (BMI) percentile above 95% for age and sex based on the Centers for Disease Control Growth Charts, any chronic illness requiring regular medication, or vitamin D deficiency (25OHD <20 ng/ml), as established by the Institute of Medicine for bone health (28). This criterion was assessed at the baseline visit. After finding many children with low vitamin D in the baseline visit (29), the protocol was amended to provide vitamin D supplements to those children for 6-8 weeks and once 25(OH)D was >20 ng/ml, they were randomized into the study.

Supplements

Participants were randomized sequentially using a computer-generated block randomization list into four groups: SCF (12 g/d), SCF + calcium (12 g/d of SCF + 600 mg/d of elemental calcium), Placebo (12 g/d of maltodextrin); or Placebo + calcium (12 g/d of maltodextrin + 600 mg/d of elemental calcium). SCF and the maltodextrin were donated in part by Tate & Lyle PLC (Hoffman Estates, IL) and the calcium (in the form of calcium lactate gluconate) was purchased from Stauber

Fullerton, CA. Supplements were pre-mixed in our diet preparation lab at FIU by a dedicated research team not involved in the assessments and delivered to participants in large white canisters of the same size and weight with a color-coded lid for a 3-month supply. Participants were instructed to consume 1 scoop of product diluted in 8-10 ounces of liquid twice per day. The study supplements were tested several times per year for microbiology integrity (aerobic plate count, coliforms, E. coli, Salmonella, yeast, and mold) by an independent external laboratory.

To promote retention, participants were given the choice of either adding the supplement to their usual beverage (non-carbonated) or to be pre-mixed in our food lab with Kool-Aid (donated by Kraft). Several flavors were offered, and they could change the flavor every 3 months. We also provided a study water bottle to facilitate taking it to school, travel, or extracurricular activities. We also sent motivational text messages about the importance of taking the supplement, how to establish the habit of taking it daily, and ideas to vary the supplement using an automated one-way text message provider. The text messages were sent twice per week for the first 6 weeks and then the frequency was reduced to every 3 weeks until the end of the study. We provided enough supplement in each canister to share with family members.

Compliance was carefully monitored during the trial and recorded in different ways. We initially developed an app to record compliance daily, but after discussing with parents their use, this was changed to a weekly survey sent by text. We also provided a paper calendar as an alternative. We asked families to record the number of supplements consumed per day (2, 1, or 0). Parents received extra compensation for monitoring supplement intake every 3 months. In addition, they were asked to complete a short questionnaire about the study supplement intake at every visit (3, 6, 9 and 12 months). Lastly, we reviewed compliance at every visit verbally. There was a dedicated person compiling the various sources of compliance information to identify when data was missing and if we needed to contact parents to discuss low compliance.

Measurements

As previously described (25), the research team was blinded to the supplement type. Participants were asked to complete three visits (baseline, 6 months, and 12 months) at our FIU labs to undergo anthropometrics and a bone scan, and complete health questionnaires. Also, participants were asked to provide a fasting blood sample, a 24-h urine collection, and a fecal sample at baseline and

12 months. We also visited participants at their home or other convenient place for the 3- and 9-months visits to deliver more supplements and complete health questionnaires.

General health and socio-demographics: this included parental age, sex, education, and medical history and children's age, sex, self-reported pubertal maturity using Tanner staging (30) and menarche date (if applicable), fracture(s) history, use of medications, use of alcohol and tobacco, sleep and stress.

Anthropometric measurements: weight, height, and waist circumferences were assessed by trained study staff at baseline, 6-month and 12-month following standardized protocols. Weight velocity and height velocity were calculated as the difference in weight or height, divided by the difference in age between consecutive annual study visits. Height velocity <0 cm/year was assumed to reflect a measurement error after reaching adult height and was recoded to 0.

Bone mass: Whole body and spine BMC and BMD were assessed using a Hologic dual-energy X-ray absorptiometry (DXA) scan at our FIU DXA Lab at baseline, 6-month and 12-month following standardized protocols. All scans were performed by trained personnel, with the Florida Department of Health Certification for Basic X-ray machine operator.

Blood sample: a fasting blood sample (15 ml each) was collected at baseline and 12-months by venipuncture by research trained phlebotomists. Samples were immediately centrifuged; part was sent to a commercial lab for 25(OH)D, calcium, phosphorus, and creatinine. The rest was stored at -80°C for future analyses.

Urine sample: a 24-h urine sample was collected at baseline and 12-months and analyzed by a commercial lab for calcium, phosphorus, and creatinine.

Diet: Three 24-h recalls were collected at baseline, and a 24-h recall was collected at 3, 6, 9, and 12 months. Dietary recalls were analyzed using the Nutrition Data System for Research (NDSR) software. Total energy intake and intakes of protein, calcium, vitamin D were calculated to be used as covariates in the statistical analyses.

Physical activity: This was collected at each visit using the International Physical Activity Questionnaire (IPAQ) (31) and used as a covariate in the statistical analyses.

Gastrointestinal symptoms: This was recorded every 3 months with a survey asking participants for abdominal pain, bloating, flatulence or diarrhea.

Statistical plan

Sample size was calculated for the primary outcome (change in whole-body BMC over 1 year between SFC and control) based on a conservative clinically meaningful standardized effect size (32), as when the study started, there were no previous studies assessing the effects of SCF on bone. For an alpha level of 0.05, 40 in each group provides 80% power to detect a medium effect size of 0.5 units of standard deviation (33) in BMC between any of the active treatment groups compared to placebo. This was inflated by >30% for non-eligible rate due to vitamin D deficiency (10%) plus drop-out rate similar to rates in our previous trials among adolescents (20%) (34–38). All power calculations were performed with PASS2019 (39).

The main analyses will be performed on an intention-to-treat basis. Data was examined for outliers and normality. Descriptive statistics included means, medians, standard deviations, and ranges for continuous variables and frequencies and proportions for categorical variables. ANOVA and chi-square test were used to compare means and proportions by treatment group. We used the same analytical methods to examine potential differential attrition by treatment group. We compared characteristics and determined missing data mechanism between study completers and those with missing outcome data, using two-sample t-test for continuous and chi-square test for categorical variables. For the primary analysis, percent change from baseline in whole-body BMC after one year of supplement was compared between the two groups using analysis of covariance, adjusted for baseline age, sex, Tanner stage (puberty status), weight velocity and height velocity. Data was analyzed using SPSS. Effects were considered significant at the alpha level of 0.05.

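### Children repleted for vitamin D deficiency before randomisation were admitted by amendment, but the primary ANCOVA has no term for them and no analysis without them is planned

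*Combined protocol and SAP*

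**What the plan says.** All references are to the combined protocol and SAP.

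- **Study population.** The exclusion list includes "vitamin D deficiency (25OHD <20 ng/ml), as established by the Institute of Medicine for bone health", assessed at the baseline visit. Many children were then found to be low, and "the protocol was amended to provide vitamin D supplements to those children for 6-8 weeks and once 25(OH)D was >20 ng/ml". Allocation to an arm came only after this repletion. The number of such children is not given.
- **Supplements.** "Participants were randomized sequentially using a computer-generated block randomization list into four groups". No stratification factor and no block size are named.
- **Statistical plan.** The primary ANCOVA takes the one-year percent change in whole-body BMC as its outcome and sets two groups against each other. The model is described as "adjusted for baseline age, sex, Tanner stage (puberty status), weight velocity and height velocity". Serum 25(OH)D, repletion and amendment period are all absent. No subgroup or sensitivity analysis by vitamin D history is described.
- **Measurements, Diet.** Vitamin D intake is named as a covariate for the statistical analyses. This is dietary intake, not serum status or repletion history, and it is not in the primary model's list.

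**The concern.** The plan itself treats 25(OH)D below 20 ng/ml as relevant to bone, which is the trial's primary outcome. Under the first rule such children did not enter. Under the amended rule they enter after a vitamin D course, so vitamin D history becomes a pre-randomisation characteristic that varies between children and could be related to the outcome.

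The analysis text does not take this up. Three things are at stake:

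- If repleted children gain BMC at a different rate, the residual variance is larger than it need be.
- Without stratification or adjustment, a chance difference in the repleted share between arms passes into the estimate.
- The reader gets no planned result for the children who would have qualified under the first rule.

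**Working it through.** **The plan's own figure.** The Statistical plan gives 40 per group for 80% power at 0.5 SD and alpha 0.05, without saying whether the test is one- or two-sided. For a two-sided comparison of two means, n = 2(1.96 + 0.84)²/0.5² ≈ 63 per group, and 40 per group gives 60.9% power. One-sided, 40 per group gives 72.3%. The 80% is reached only with a covariate R² of about 0.36, which is not stated. This is a separate matter and the present point does not depend on it. Below, 60.9% serves only as the reference for power.

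**Inputs.**

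- From the plan: 40 per group and a target effect of 0.5 SD.
- Assumed, because the documents give neither: repleted share p = 10–40%, and difference d = 0.25–0.5 SD in percent BMC change between repleted and never-deficient children. The low end of p equals the 10% that the sample-size text allows for vitamin D ineligibility. Nothing in the documents fixes the high end.
- The Statistical plan speaks of two groups although four are randomised, so both 40 v 40 and a pooled 80 v 80 are shown.

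**Step 1: precision.** Leaving out a binary factor multiplies the outcome variance by 1 + p(1−p)d².

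- Low end: 0.1 × 0.9 × 0.25² = 0.0056, so the SD is multiplied by √1.0056 = 1.003.
- High end: 0.4 × 0.6 × 0.5² = 0.06, so the SD is multiplied by √1.06 = 1.030.

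The SD inflation is therefore about 0.3–3%. At 40 v 40 and 0.5 SD, power falls from 60.9% to no lower than about 58.4%. With wider assumptions (p = 10–50%, d = 0.2–0.8 SD), the inflation is 0.2–7.7% and power is 60.7–54.6%.

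**Step 2: chance imbalance.** The standard error of the between-arm difference in repleted share is √(2p(1−p)/n). At p = 30%:

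| Comparison | SE of difference in share | 20-point gap in SEs | Approximate two-sided probability |
|---|---|---|---|
| 40 v 40 | √(0.42/40) = 10.2 points | 1.95 | 0.05 |
| 80 v 80 | √(0.42/80) = 7.2 points | 2.8 | 0.006 |

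The shift in the estimate is the imbalance times d. At 40 v 40, a one-SE imbalance gives 0.102 × 0.25 = 0.026 SD to 0.102 × 0.5 = 0.051 SD. A 20-point gap at the top of the assumed range gives 0.20 × 0.5 = 0.10 SD. The standard error of the treatment contrast itself is √(2/40) = 0.22 SD, so even that case is under half of one standard error.

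**Step 3: what the restricted analysis would hold.** At p = 10–40%, 4–16 of 40 children per arm are repleted and 36–24 remain. Intervals widen by √(40/36) = 1.05 to √(40/24) = 1.29, that is by about 5–29%.

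**The case against.** The strongest reply is that this is an optional covariate of unknown strength. Both inputs to the size calculation are assumed, the precision loss is small, and chance imbalance has expectation zero and is already reflected in the confidence interval. Sequential blocking also keeps the arms close to balanced before and after the amendment. Most of this stands, and it limits the size of the point. Blocking does not, however, balance repleted against never-deficient children within the period after the amendment. Counts of repleted children may also appear in the cited publications, which were not available for this review. That would answer the reporting part but not the analysis part.

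A reader might infer more than the documents support:

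- *That two populations with different bone accrual are pooled.* No section reports a difference in accrual, and every child was above the plan's cutoff when randomised. The groups are known to differ only in vitamin D history.
- *That the trial cannot speak to vitamin-D-sufficient children.* By the plan's own cutoff, all those randomised were sufficient. Only a contrast between never-deficient and repleted children is left open.
- *That vitamin D was a co-treatment during the trial.* The course came before randomisation and did not depend on arm. Nothing says that it continued.
- *That a 20-point imbalance would be ordinary.* At 40 v 40 it is about a 1-in-20 event, and at 80 v 80 it is rare.
- *That using the pre-repletion 25(OH)D as the baseline value distorts the results.* No described analysis uses serum 25(OH)D, so the choice changes no described estimate.

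**Conclusion.** The point holds as a modest gap in adjustment and reporting. The plan admits children with a history it had treated as bone-relevant. It then describes no stratification on that history, no adjustment for it, and no analysis without these children. The randomised comparison remains unbiased in expectation.

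Under the stated assumptions, both the precision loss and the likely shift from chance imbalance are small against the uncertainty of the treatment contrast. The true size cannot be settled until the number of repleted children is known. The case for acting rests mainly on the low cost and on the missing check in the originally eligible children.

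**What to change.** 1. Add to the primary ANCOVA a yes/no indicator for children who were deficient at baseline and repleted before randomisation. It is fixed before allocation, and the trial records must hold it because randomisation depended on it.
2. Report the number of repleted children in each arm.
3. Specify one sensitivity analysis restricted to never-deficient children, who are the population of the first criterion.

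The document is dated 09/26/2025 and describes the analysis partly in the past tense. If the primary analysis has already been run, keep it as the primary result and report the adjusted and the restricted analyses as post hoc sensitivity analyses.

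The cost is one degree of freedom, a few lines of SAP text, and wider intervals in the restricted analysis. Separate effect estimates in repleted children are not recommended as a basis for conclusions, because with 4–16 such children per arm of 40 they would be too imprecise.

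### On its stated inputs, 40 per group gives about 60% power for a 0.5 SD pairwise difference, not 80%; 80% needs 64 per group

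*Combined protocol and SAP*

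**What the plan says.** The sample-size paragraph of the Statistical plan names the primary outcome as the one-year change in whole-body BMC. It gives its result in one sentence, at alpha 0.05: "40 in each group provides 80% power to detect a medium effect size of 0.5 units of standard deviation (33) in BMC". The comparison is specified as "in BMC between any of the active treatment groups compared to placebo", that is, two arms at a time. The Supplements section confirms four randomized arms, one of them placebo alone.

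The next sentence enlarges the 40: "This was inflated by >30% for non-eligible rate due to vitamin D deficiency (10%) plus drop-out rate", with drop-out put at 20%.

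The paragraph gives no sidedness, no covariate R-squared or correlation, no pooling of arms and no multiplicity adjustment. It names the software (PASS2019) but not the procedure. The following paragraph makes the primary analysis an ANCOVA of percent change between two groups, adjusted for age, sex, Tanner stage, weight velocity and height velocity. It ends: "Effects were considered significant at the alpha level of 0.05".

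**The concern.** A two-arm comparison at 0.5 SD, two-sided 5% alpha and 80% power is a textbook case that needs a little over 60 per arm. A figure of 40 stands out at once.

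This sentence is the only justification of sample size for the primary outcome, and the plan presents the target effect as conservative and clinically meaningful. A reader who takes 80% at face value will see a null SCF-versus-placebo result as fairly strong evidence against a 0.5 SD effect. If power is nearer 60%, such a result is much weaker evidence, because a true effect of that size would be missed about two times in five.

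**Working it through.** **Inputs, all from the Statistical plan.** n = 40 per arm; standardized difference d = 0.5 (so SD = 1); alpha = 0.05; stated power 80%; one active arm versus placebo, equal arm sizes. Sidedness is not stated. Two-sided is assumed first, and one-sided is tried below.

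**1. The plan's own figure.** For a two-sample t-test the noncentrality is d × √(n/2) = 0.5 × √20 = 2.236, on 2 × 40 − 2 = 78 degrees of freedom, with two-sided critical value 1.991.

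- Noncentral t: power = **59.8%**.
- Normal approximation: Φ(2.236 − 1.960) = Φ(0.276) = 60.9%.

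The stated 80% is not reproduced.

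**2. Sample size for 80%.** Normal approximation: n = 2 × (1.960 + 0.842)² / 0.5² = 62.8, so 63 per arm. Noncentral t: 63.8, so **64 per arm**.

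**3. Difference detectable with 80% power at n = 40.** Noncentral t: **0.634 SD**.

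**4. Other readings of the sentence** (d = 0.5 unless shown; t or F distribution):

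| Reading | Power | Needed for 80% |
|---|---|---|
| One-sided t-test, 40 v 40 | 71.6% | 51 per arm |
| Four-group ANOVA, f = 0.25, N = 160 | 74.9% | 45 per arm |
| Four-group ANOVA, one arm differs by 0.5 SD, N = 160 | 61.1% | – |
| Two arms pooled v one, 80 v 40 | 72.6% | – |
| Three active arms pooled v placebo, 120 v 40 | 77.7% | – |
| SCF arms v non-SCF arms, 80 v 80 | 88.2% | – |

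The nearest is 120 v 40 (78.2% by the normal approximation), but pooling all active arms is not what the sentence describes. The 80 v 80 reading overshoots; its detectable difference at 80% power is 0.446 SD. The plan makes no multiplicity adjustment. If alpha were split over the three active-versus-placebo comparisons, pairwise power would be 42.1%.

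**5. Does the inflation explain it?** It is applied after the 40 and is meant to be used up by ineligibility and drop-out. The plan says only that it exceeds 30%, so these are illustrations:

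- 40 × 1.30 = 52 per arm; after 20% drop-out, 52 × 0.80 = 41.6, power 61.5%.
- 52 with nobody lost: 71.4%.
- 40 / 0.70 = 57.1, so 58 with nobody lost: 76.1%.

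**6. Does covariate adjustment explain it?** Covariates that explain a share R² of the variance shrink the residual SD to √(1 − R²). For 40 per arm to suffice, 0.5/√(1 − R²) must equal 0.634, so R² = 1 − (0.5/0.634)² = **0.38**. Losing five degrees of freedom for the covariates hardly matters: R² = 0.38 on 73 degrees of freedom gives 80.0%. With a one-sided test the detectable difference is 0.561 SD, and the R² needed falls to 1 − (0.5/0.561)² = 0.21.

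**The case against.** The best defence is that the planned primary analysis is not an unadjusted t-test. It is an ANCOVA with age, sex, Tanner stage and two growth-velocity terms, and for bone accrual in adolescents an R² near 0.38 is plausible. With a one-sided test about 0.21 would do. The PASS procedure is not given and the plan refers to a separate publication for trial details, so an undisclosed input cannot be ruled out. This part stands: the software may have been given something that the text omits. It does not save the sentence, which expresses the effect simply in SD units and mentions no covariates. Either the figure is wrong or the input that decides it is missing.

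Second, the same paragraph opens by describing the comparison as SCF against control, and the analysis paragraph speaks of two groups. If that means the two SCF arms against the two non-SCF arms, power for 0.5 SD is 88% and the primary comparison is better powered than claimed. This also stands, and it limits the shortfall to the pairwise comparisons. It does not reproduce 80%, and the power sentence explicitly refers to each active arm against placebo.

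Third, recruitment is over, so no estimate, interval or p-value changes. That is true, and nowhere does the plan say that it will interpret pairwise results through this figure. What is affected is how a reader weighs a null result.

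**Conclusion.** The concern holds. For the comparison that the sentence names, power is 59.8% rather than 80%, a shortfall of 20 percentage points. The type II error is about 40% rather than 20%. The sample size for 80% is 64 per arm rather than 40, and the effect that 40 per arm can detect with 80% power is 0.63 SD rather than 0.5 SD.

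These figures assume a two-sided test, equal arms and no covariate gain. Dropping two-sidedness alone gives 71.6%. Reaching 80% in the pairwise comparison requires an unstated covariate R² of about 0.38 (two-sided) or 0.21 (one-sided). The conclusion does not extend to a pooled SCF-versus-no-SCF comparison, which has 88% power for 0.5 SD with 80 per side.

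**What to change.** Correct the power sentence in one of three ways.

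1. Restate the pairwise claim: with 40 per group and two-sided alpha 0.05, power is about 60% for a 0.5 SD difference between one active arm and placebo, and 80% for 0.63 SD.
2. If the primary contrast is the SCF main effect across the 2×2 design, attach the claim to it: 80 with SCF versus 80 without gives 88% power for 0.5 SD and 80% for 0.45 SD. Say that the pairwise comparisons have less.
3. If covariate adjustment or a one-sided test was assumed, state the sidedness, the PASS procedure and the R² used (about 0.38 if two-sided), with its source.

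This is a wording change only, with no further enrolment and no change to the analysis. The cost is that, under the first two options, the stated pairwise power becomes less favourable.

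### The primary endpoint is defined in three ways and the primary comparison is between two unnamed groups in a four-arm trial, with no testing order, so a 5% false-positive rate is not assured

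*Combined protocol and SAP*

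**What the plan says.** **Endpoint.** In Study rationale and overall design, "the primary outcome was change in total and spine BMC between baseline and 6 months and between baseline and 12 months". That is two sites by two intervals, so four outcomes. The sample-size paragraph of the Statistical plan has one: "primary outcome (change in whole-body BMC over 1 year between SFC and control" (SFC is presumably SCF). The analysis paragraph also has one, on a different scale: "percent change from baseline in whole-body BMC after one year of supplement was compared between the two groups using analysis of covariance".

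**Arms.** Under Supplements, "Participants were randomized sequentially using a computer-generated block randomization list into four groups": SCF, SCF plus calcium, placebo, and placebo plus calcium.

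**Contrast.** Besides SCF against control, the sample-size paragraph says that "40 in each group provides 80% power to detect a medium effect size of 0.5 units of standard deviation" "in BMC between any of the active treatment groups compared to placebo". The analysis paragraph compares two groups that it does not name.

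**Error control.** The only rule is "Effects were considered significant at the alpha level of 0.05". No hierarchy, split of alpha or adjustment appears.

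**Timing.** One sentence looks forward ("The main analyses will be performed on an intention-to-treat basis"). Most of the rest is in the past tense, and the document is dated 09/26/2025.

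**The concern.** A reader cannot tell which single result decides the trial. With four arms, a two-group ANCOVA must either leave arms out or pool them, and the plan does neither explicitly. One SCF arm against placebo, both SCF arms against placebo alone, and SCF averaged over calcium are different questions with different power. Taken literally, the analysis paragraph also leaves three of the four declared primary outcomes without a primary analysis.

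The false-positive rate is at stake. It is 5% only if one endpoint and one contrast were fixed before the data were seen. If the contrast was chosen later, or if other declared outcomes or arms could also be reported as primary, it is higher.

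**Working it through.** **Inputs.** From the Statistical plan: 40 per group, effect 0.5 SD, alpha 0.05, stated power 80%. Sidedness and the correlations between endpoints are not given. I assume equal allocation (from 40 in each group) and show both sidedness options and a range of correlations.

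**1. Can the stated 80% identify the contrast?** Power comes from the noncentral t distribution with noncentrality 0.5 / √(1/n₁ + 1/n₂) and n₁ + n₂ − 2 degrees of freedom, without covariate adjustment.

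| Reading | Noncentrality | Two-sided | One-sided |
|---|---|---|---|
| One arm v placebo, 40 v 40 | 0.5/√0.05 = 2.236 | 59.8% | 71.6% |
| Both SCF arms v placebo alone, 80 v 40 | 0.5/√0.0375 = 2.582 | 72.6% | 82.2% |
| Both SCF arms v both placebo arms, 80 v 80 | 0.5/√0.025 = 3.162 | 88.2% | 93.4% |

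None gives 80%. The smallest effect with 80% two-sided power is 0.63 SD at 40 v 40 and 0.45 SD at 80 v 80. For 40 v 40 two-sided to reach 80%, the covariates would have to explain about 38% of the variance (80 − 2 − 5 = 73 degrees of freedom), which is not stated. The power statement therefore does not show which contrast was meant.

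**2. One endpoint, several contrasts, each at two-sided 0.05.** Contrasts that share a placebo arm have correlation 0.5. The chance of at least one false positive among k of them is 1 − ∫ φ(x)[Φ(x + z√2) − Φ(x − z√2)]^k dx, with z = 1.96.

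- Two SCF arms v placebo: 9.1%.
- Three active arms v placebo: 12.5%.
- Best of four readings of the unnamed pair (SCF v placebo; SCF + calcium v placebo + calcium; pooled SCF v pooled placebo; SCF + calcium v placebo), by simulation: 14.2%.

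**3. Four declared endpoints, each at 0.05.** Simulation with 400,000 draws, two sites by two times:

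| Assumed site / time correlation | One contrast | Two SCF arms | Three active arms |
|---|---|---|---|
| 0 / 0 | 18.6% | 31.6% | 41.5% |
| 0.5 / 0.5 | 16.2% | 27.7% | 36.8% |
| 0.7 / 0.71 | 13.7% | 23.6% | 31.6% |
| 0.9 / 0.9 | 9.8% | 17.3% | 23.3% |

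The exact value for the first cell is 1 − 0.95⁴ = 18.5%.

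**4. Does leaving calcium out of a pooled analysis matter?** Little. With an assumed calcium effect of 0.5 SD (200,000 draws), power is 86.8% without the term and 88.0% with it; type I error is 4.3% and 5.0%.

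**The case against.** The strongest reply is that the analysis paragraph specifies one test: one endpoint, one time, one ANCOVA, alpha 0.05. The sample-size paragraph uses the same site and time. Outcomes that are never tested as primary add no false positives, so it is inconsistent to say that three outcomes go unanalysed and also to count them in the error rate. That is right for a literal reading. The multi-endpoint rates apply only if the outcomes declared in the design section are in fact tested as primary.

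Other points also carry weight:

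- The zero-correlation figures are outer bounds. The 6-month change is part of the 12-month change, and both sites are measured in the same children.
- The three-arm figures require placebo plus calcium to count as active, although the stated aim concerns SCF.
- Change may be loose wording for percent change.
- Covariate adjustment could raise power. An R² of about 0.17 would suffice for 80 v 40 two-sided, and about 0.21 for 40 v 40 one-sided.
- The design section refers to a published account of the trial, not available here, which may name the contrast and the testing order.

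None of this identifies the two groups. The pooled SCF comparison is a plausible guess, but the sample-size paragraph describes active groups against placebo at 40 each, which is not pooled. If the published account settles the matter, this document still contradicts itself, and citing that account would be part of the repair.

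**Conclusion.** The concern holds. The conflicting statements are complete sentences, so this is not a gap left by text extraction. The primary endpoint differs between sections in number and scale, and the primary contrast cannot be identified from the text.

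The claim is that 5% is not assured, not that it was exceeded. With one contrast fixed in advance, the rate is 5%. With the contrast left open, it is about 14% on a single endpoint. If the four declared endpoints are all tested at 0.05, it is about 14%, 24% or 32% for one, two or three contrasts, assuming correlations of 0.7 between sites and 0.71 between times. The choice of contrast also moves two-sided unadjusted power from 60% to 88%. The missing calcium term is a minor matter by itself.

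**What to change.** Use one primary statement in every section, giving endpoint, time, scale, contrast and sidedness. A natural choice is the SCF main effect, both SCF arms against both placebo arms, on 12-month whole-body BMC. It would come from an ANCOVA over all four arms with SCF and calcium as factors, at two-sided 0.05. Then:

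- report the SCF-by-calcium interaction with its confidence interval;
- place spine and 6-month BMC in a fixed sequence or a Holm procedure, or relabel them secondary;
- report single active arms against placebo as secondary, with Dunnett adjustment;
- restate power for the chosen contrast (80 v 80 unadjusted: 88% for 0.5 SD, 80% for 0.45 SD);
- state which definition was fixed before unblinding and in which dated record, and label any later choice post hoc.

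The cost is wording, one model factor, a new power statement and a search for the record. If no record exists, rewording cannot restore error control and the contrast has to be called post hoc. Spine, 6-month and single-arm results would face stricter thresholds or lose primary status. The pooled effect is an average over calcium, and the interaction is estimated poorly at 40 per arm: the 95% half-width is 1.975 × √(4/40) = 0.62 SD.

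Keeping all four endpoints primary with Bonferroni (0.0125 each) would leave about 75% power per endpoint at 80 v 80 and 40% at 40 v 40 (normal approximation, 0.5 SD), so a single primary endpoint is the cheaper course.
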